## List of Abbreviations

|       |   |
|-------|---|
| AED   | Anti-epileptic drug                                 |
| CBD   | Cannabidiol   |
| CBG   | Cannabigerol  |
| CBDV  | Cannabidivarin                                      |
| CBC   | Cannabichromene                                     |
| CYP   | Cytochrome P  |
| GABA  | Gamma-aminobutyric Acid                             |
| LFP   | Local field potential                               |
| LFT   | Liver function tests                                |
| MES   | Maximal Electroshock                                |
| PESQ  | Pediatric Epilepsy Side Effects Questionnaire       |
| PTZ   | Pentylentetrazol                                    |
| QOLCE | Quality of Life in Childhood Epilepsy Questionnaire |
| SUDEP | Sudden Unexplained Death in Epilepsy                |
| THC   | Delta-9-Tetrahydrocannabidiol                       |
| VNS   | Vagus nerve stimulator                              |

## Study Summary

|                                       |  |
|---------------------------------------|--|
| Title                                 | Cannabinoid Therapy in Medically Refractory Pediatric Epilepsy – Phase 1: Dosing and Tolerability Study of a Cannabidiol-Rich Whole Plant Extract of Cannabis.   |
| Short Title                           | Cannabinoid Therapy for Pediatric Epilepsy   |
| Phase                                 | 1  |
| Methodology                           | Open-label Intervention  |
| Study Duration                        | 20 weeks to primary analysis with continued follow-up until 64 weeks completed   |
| Study Center                          | The Hospital for Sick Children, Toronto Ontario  |
| Objectives                            | To determine the tolerability and optimal dose of 50:1 ratio CBD:THC Cannabis extract as an adjunct treatment in children with severe drug resistant epilepsy  |
| Number of Subjects                    | 20   |
| Diagnosis and Main Inclusion Criteria | Patients with Dravet Syndrome

Between ages of 1 and 18 years old male or female

Must have failed 2 AEDs at therapeutic doses and be on current regimen of 1-4 AEDs which have been stable doses for 4 weeks  |
| Study Product, Dose, Route, Regimen   | TIL-TC150 Oil is the study product
The active ingredients in TIL-TC150 Oil are THC and CBD, present in a 1:50 ratio. These active ingredients are derived from Cannabis sativa L. strains produced by Tilray and suspended in a grape seed oil. This suspension is administered at a dose of 2mg/kg/day CBD divided BID and titrated up to a maximal dose of 16mg/kg/day CBD (or maximal tolerated). |
| Duration of Administration            | Study period: primary safety and outcome data at 20 weeks with longer follow-up of safety and tolerability in those who chose to continue after the 20-week period and will be followed up to 64 weeks.  |
| Reference Therapy                     | None   |
| Statistical methodology               | The primary aims of this study are to determine the maximal tolerated dose of TIL-TC150 Oil Cannabis Extract in children with drug resistant epilepsies. Descriptive statistics will be used to quantify the frequency and severity of adverse events that are   |

|  |  |
|--|--|
|  | reported for the various dosages that are employed |
|--|--|

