### 5.2 Treatment Regimen

Each participant will start the treatment with a dose of 2mg/kg/day CBD given in two equal doses each day. The first dose will be given during the Baseline (Week 0) visit. Following this dose the participant will be observed by study personnel for a period of 2 hours. The participant's parent/legal guardian will increase the participant's dose by 2mg/kg/day CBD every 7 days as tolerated, to a maximal dose of 16mg/kg/day CBD. Once optimal dose is determined for each participant they may continue the treatment for the duration of study follow-up and thereafter it will be continued if wished by participants.

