|                                 | 1             | Telephone and/ or email contact by study team to determine dosing and tolerability   | Once tolerance ensured, increase dose to 4mg/kg/day CBD divided twice daily  |

|    |  |   |
|----|--|---|
| 2  | Clinic visit – tolerance review, adverse events,; physical and neurological exam; parent/legal guardian to complete PESQ; seizure diary review   | Once tolerance ensured, increase to 6mg/kg/day CBD divided twice daily  |
| 3  | Telephone and/ or email contact by study team to determine dosing and tolerability   | Once tolerance ensured, increase to 8mg/kg/day CBD divided twice daily  |
| 4  | Clinic visit – tolerance review, adverse events; physical and neurological exam; parent/legal guardian to complete PESQ; seizure diary review; bloodwork   | Once tolerance ensured, increase to 10mg/kg/day CBD divided twice daily |
| 5  | Telephone and/ or email contact by study team to determine dosing and tolerability   | Once tolerance ensured, increase to 12mg/kg/day CBD divided twice daily |
| 6  | Telephone and/ or email contact by study team to determine dosing and tolerability   | Once tolerance ensured, increase to 14mg/kg/day CBD divided twice daily |
| 7  | Telephone and/ or email contact by study team to determine dosing and tolerability   | Once tolerance ensured, increase to 16mg/kg/day CBD divided twice daily |
| 8  | Clinic visit – tolerance review, adverse events; physical and neurological exam; parent/legal guardian to complete PESQ and QOLCE; seizure diary review; bloodwork performed once child is at target / maximal tolerated dose (any stage from week 8-16) | If tolerated, dose to continue at 16mg/kg/day CBD divided twice daily   |
| 10 | Telephone and/ or email contact by study team to determine dosing and tolerability   | If tolerated, dose to continue at 16mg/kg/day CBD divided twice daily   |
| 12 | Clinic visit – tolerance review, adverse events; physical and neurological exam; parent/legal guardian to complete PESQ; seizure diary review; bloodwork performed once at target / maximal tolerated dose (if not done previously)                      | If tolerated, dose to continue at 16mg/kg/day CBD divided twice daily   |
| 14 | Telephone and/ or email contact by study team to determine dosing and tolerability   | If tolerated, dose to continue at 16mg/kg/day CBD divided twice daily   |

|                                      |       |  |   |
|--------------------------------------|-------|--|---|

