|                                      | 16    | Clinic visit – tolerance review, adverse events; physical and neurological exam; parent/legal guardian to complete PESQ and QOLCE; seizure diary review; bloodwork performed once at target / maximal tolerated dose (if not done previously)  | If tolerated, dose to continue at 16mg/kg/day CBD divided twice daily   |
| Primary Analysis              | 16-20 | Telephone and/ or email contact by study team at 18 weeks to determine dosing and tolerability

Psychologist will arrange for parent/caregiver to complete a Vineland assessment

Participant parent/legal guardian completion of seizure diary during this 4 weeks; 24 hour ambulatory EEG. Collection of seizure diary reported seizure frequency. | If tolerated, dose to continue at 16mg/kg/day CBD divided twice daily   |
|                                      | 20    | If tolerated, and participant parent/legal guardian wishes to continue study product dose to continue at 16mg/kg/day CBD divided twice daily   |   |
| Longitudinal follow-up period | 28    | Clinic visit – tolerance review; physical and neurological exam; parent/legal guardian to complete PESQ and QOLCE; seizure diary review;   | If tolerated, and participant parent/legal guardian wishes to continue, dose to continue at 16mg/kg/day CBD divided twice daily |
|                                      | 40    | Clinic visit – tolerance review; physical and neurological exam; parent/legal guardian to complete PESQ; seizure diary review;

Follow up bloodwork performed once (any stage from week 40-64)   | If tolerated, and participant parent/legal guardian wishes to continue, dose to continue at 16mg/kg/day CBD divided twice daily |
|                                      | 52    | Clinic visit – tolerance review; physical and neurological exam; parent/legal guardian to complete PESQ and QOLCE; seizure diary review;

Follow up blood work performed once (if not done previously)

During 52-64 weeks psychologist will arrange for parent/caregiver to complete a Vineland   | If tolerated, and participant parent/legal guardian wishes to continue, dose to continue at 16mg/kg/day CBD divided twice daily |

|  |    |   |   |
|--|----|---|---|
|  |    | assessment  |   |

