## **8. Statistics**

### **8.1 Statistical Method**

This is an observational study. The primary aims of this study are to determine the tolerability of the study treatment in a cohort of children with medication resistant epilepsy due to Dravet syndrome. As such, there are no formal statistical methods required, rather descriptive statistics will be presented to quantify dosing tolerability and frequency of adverse events. All participants will be analyzed regardless of dose achieved or duration of study completed, according to intention to treat analysis. The study data will be entered into the REDCap database for analysis.

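### An adverse-event table by dosage cannot be read as a dose-response, because each dose is reached only by children who tolerated the lower ones

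*Combined protocol and SAP*

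**What the plan says.** The Study Summary names the maximal tolerated dose as the primary aim. Under statistical methodology it plans descriptive statistics for the frequency and severity of adverse events "reported for the various dosages that are employed". Section 8.1 states that "descriptive statistics will be presented to quantify dosing tolerability and frequency of adverse events" and analyses every participant whatever dose was achieved, but it does not repeat the by-dosage wording. Section 3.4 makes the highest safely tolerated dose the primary endpoint.

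Dose follows tolerance. Section 5.2 has the parent or guardian "increase the participant's dose by 2mg/kg/day CBD every 7 days as tolerated, to a maximal dose of 16mg/kg/day CBD". The schedule table in 5.8 attaches the same condition to each step, for example "Once tolerance ensured, increase to 6mg/kg/day CBD divided twice daily" at Week 2 and "Once tolerance ensured, increase to 16mg/kg/day CBD divided twice daily" at Week 7. From Week 8 it reads "If tolerated, dose to continue at 16mg/kg/day CBD divided twice daily".

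The document does not define the denominator at each dose, whether frequency means events per child-week or children with any event, the dose to which an event is assigned, or how children who stop escalating are shown. There is no comparator (Study Summary), and withdrawals are not replaced (4.4.3).

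**The concern.** A child's dose is partly a result of how well that child tolerated the drug. Children who could not go past 8 or 10 mg/kg/day contribute nothing to the 16 mg/kg/day row, so that row describes those who got through seven conditional increases. The lower rows describe a more mixed group. A difference between rows then combines the effect of dose with the effect of who was left. Time at dose differs as well: a child on schedule spends one week at each lower step and most of the primary period at the top.

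A reader looking for the highest tolerated dose will naturally compare rows. Section 1.4 reports that gastrointestinal effects were more frequent at higher doses in the cited open-label study, so a dose gradient is a real possibility. A flat or falling table could hide it, and an unadjusted count could exaggerate it.

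**Working it through.** **Plan's own figures.** The document gives no adverse-event rate, between-child spread or sample-size calculation (8.2), so there is no figure to reproduce. The schedule gives dose at Week w = 2 + 2w mg/kg/day, so 2 + 2×7 = 16 at Week 7. Time at 16 to Week 20 is 20 − 7 = 13 weeks, against 1 week at each lower step. Section 3.2 puts the last increase at Week 8, which would leave 20 − 8 = 12 weeks. The Week 12 visit text in 5.6 gives a maximal dose of 8 mg/kg/day where other sections say 16. These places must be reconciled, but the argument does not depend on which holds.

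**Check 1: exact expected values, all rates assumed.** Half of 20 children are sensitive, with weekly intolerance rising linearly from 30% at 2 to 45% at 16 mg/kg/day. Half are robust, rising from 2% to 4%. A child intolerant at one dose does not enter the next. With S and R the fractions of the original group still ascending:

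- observed intolerance at a dose = (S·p_s + R·p_r)/(S + R)
- next step: S → S(1 − p_s), R → R(1 − p_r)

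At 2 mg/kg/day: 0.5×0.30 + 0.5×0.02 = 16.0%. Then S = 0.35, R = 0.49, and 20×0.84 = 16.8 children are expected to enter 4 mg/kg/day. Of those entering 16, about 4.8% are sensitive: 0.048×0.45 + 0.952×0.04 = 6.0%. Had all 20 been exposed at 16: 0.5×0.45 + 0.5×0.04 = 24.5%.

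| Dose (mg/kg/day) | 2 | 4 | 6 | 8 | 10 | 12 | 14 | 16 |
|---|---|---|---|---|---|---|---|---|
| Expected entering | 20 | 16.8 | 14.3 | 12.5 | 11.0 | 10.0 | 9.2 | 8.6 |
| Observed at dose, % | 16.0 | 14.7 | 13.1 | 11.3 | 9.5 | 8.0 | 6.8 | 6.0 |
| If all 20 exposed, % | 16.0 | 17.2 | 18.4 | 19.6 | 20.9 | 22.1 | 23.3 | 24.5 |
| Cumulative, all 20, % | 16.0 | 28.4 | 37.7 | 44.8 | 50.0 | 54.0 | 57.1 | 59.7 |

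Risk rises with dose in every child, yet the observed row falls. Other assumed mixes, from 2 to 16 mg/kg/day:

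- a quarter sensitive: observed 9.0% to 4.7%, against 9.0% to 14.3% if all were exposed
- half sensitive but milder (10% to 30%, and 2% to 6%): observed 6.0% to 11.6%, against 6.0% to 18.0%; flattened, not reversed
- identical children (5% to 20%): no bias

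**Check 2: rates per child-week to Week 20.** Simulation of 200,000 children per setting. The rate is proportional to dose in each child, so the true 16:10 ratio is 16/10 = 1.6. Assumed average rates at 10 mg/kg/day are 0.05 to 0.2 per week. A child steps back or holds after an event during titration only. Susceptibility follows a gamma distribution with mean 1; a smaller shape means a wider spread.

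| Spread between children | Observed 16:10 ratio |
|---|---|
| Gamma shape 1 | about 0.67 to 1.04 |
| Gamma shape 2 | 0.94 to 1.24 |
| Gamma shape 4 | 1.2 to 1.4 |
| None | 1.6 |

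**Check 3: trials of 20 children.** 20,000 trials per setting, assumed base rate 0.05 per week, true rate ratio 2 for 16 against 2 mg/kg/day, lognormal spread. The chance that the child-week rate at 16 falls below the pooled rate at lower doses is 0.17, 0.27, 0.55 and 0.79 for SD 0, 0.5, 1.0 and 1.5. The 0.17 at SD 0 is chance from small counts.

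**Check 4: the other measure.** If the table shows children with any event at each dose, the same trials give 48% to 73% at 16 against about 6% to 8% per lower dose. Unequal time alone can do this. At a constant 5% per week with no dose effect, one week gives 5%, and 13 weeks give 1 − 0.95^13 = 48.7%.

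**The case against.** The by-dosage phrase occurs once, in the summary. The study is single-arm and descriptive with 20 children. Section 8.1 keeps every child in the analysis, and a maximal tolerated dose is determined for each child (5.2, 5.6, 5.7). No section plans a dose-response comparison. This stands as a limit on weight: the table is not the only evidence on tolerability. It does not remove the problem. Analysing everyone keeps intolerant children in the overall summary but puts none of them in the 16 mg/kg/day row, and 8.1 specifies no other display for the primary endpoint.

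Three stronger readings are tempting, and the documents do not support them:

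- **That the bias always favours the top dose.** This needs time-adjusted rates. Counts of children with any event are pushed the other way, and the plan names no measure.
- **That intolerant children stay on a reduced dose for the rest of the study.** No section says so. Section 1.7.1 allows dose or frequency adjustment, and the Week 16 text in 5.6 and the Week 8 row of 5.8 foresee the target dose being reached late. The selection needs only that some children hold or stop.
- **That the gradient will reverse.** Reversal needs marked differences between children relative to the dose effect, and the documents give no information on that spread.

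**Conclusion.** The point holds as a statement of what the planned table can do. With child-week rates, selection flattens the gradient whenever children differ in susceptibility and can reverse it when they differ markedly; there is no bias if they are alike. With any-event percentages, longer time at 16 mg/kg/day makes that dose look worse. Under either measure the table is not a dose-response and does not by itself establish the primary endpoint.

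The sizes rest on assumed event rates, spreads and hold or step-back behaviour, so they show direction and plausible range and do not predict this trial's result. The point does not invalidate the study. It should be settled before analysis because it bears on the primary aim and a better display is available.

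**What to change.** In the Study Summary and 8.1, make the main tolerability display a step table. For each dose give:

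- children entering the dose and child-weeks at it
- adverse events, assigned to the dose at onset
- children held, reduced or stopped there for an adverse event
- the cumulative proportion of all dosed children (planned 20) not tolerating at or below that dose, with exits for other reasons censored

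The cumulative proportion is 1 − ∏(1 − d_j/n_j), where n_j children enter step j and d_j of them exit it for an adverse event. It cannot fall with dose and bears directly on the endpoint in 3.4. In Check 1 it rises to 59.7% while the by-dose row falls to 6.0%. Use an equal window, such as the first week at each step, for comparison between doses, and report longer time at 16 separately. State in advance how a child who is held and later re-escalates is counted.

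Show first-ascent time apart from later time at a held or reduced dose. State that by-dose rates are descriptive and not a dose-response.

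A paired comparison of children at a dose with the same children at their lower doses is not a remedy. Those who reach a dose are selected for few events below it. In simulations with titration-only step-back, children still on 16 had no events on lower doses in any setting, so the comparison is biased against the higher dose.

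The cost is revised wording and a longer table with small counts per step. The data are already planned: dose checks and adverse-event review at visits and contacts (5.6, 5.7), and adverse-event forms (7.3). No dosing or clinical rule changes.

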## 1. Background

### 1.1 Introduction

This is a single center study to ascertain dosing and tolerability of add-on (i.e., in addition to their standard anti-epileptic therapy) Cannabidiol in children between 12 months and 18 years with treatment-resistant epilepsy due to Dravet syndrome. Dravet syndrome is a devastating syndrome which causes medication resistant epilepsy associated with significant cognitive morbidity and frequent seizures [1-7]. In addition to the significant morbidity, children with refractory epilepsy are at risk of seizure-related mortality and Sudden Unexpected Death in an Epilepsy Patient (SUDEP) [8]. The risk of SUDEP in treatment resistant epilepsy is 1 in 150 [9]. The current armory of anti-epileptic drugs, dietary therapy and the Vagal Nerve Stimulator (VNS) device are not always successful in achieving seizure control. The healthcare costs of childhood-onset treatment resistant epilepsy are well established [10, 11]. In Dravet syndrome the severity of the epilepsy often requires frequent emergency department attendances, and hospital admissions.

#### Rationale for this study

The availability of a treatment to reduce the seizure frequency in children with Dravet syndrome (thus reducing hospital admissions) and to provide the chance of improved long term cognitive outcome, hence reducing the need for lifelong neurodisability service availability, would lead to significant savings in healthcare expenditure [12].

In addition, it is scientifically plausible that this study product would have efficacy in treating seizures in Dravet syndrome. In 80% of cases of Dravet syndrome a causative genetic mutation is detected in a Sodium channel coding gene (SCN1a mutation). Cannabinoids CBD and CBG have been shown to be potent sodium channel blockers in both human and animal models.

[figure not shown]
## 1.2 Investigational Product

The physiochemical characteristics of THC and CBD are detailed in Table 1.

| Table 1: Drug Substance Common Name | delta-9-tetrahydrocannabinol (THC) and cannabidiol (CBD)  |
|--|---|
| Chemical Name                       | THC: IUPAC ID: (-)-trans- $\Delta^9$ -tetrahydrocannabinol; IUPAC ID: (-)-(6aR,10aR)-6,6,9-trimethyl-3-pentyl-6a,7,8,10a-tetrahydro-6H-benzo[c]chromen-1-ol.
CBD: IUPAC ID: 2-[(1R,6R)-6-isopropenyl-3-methylcyclohex-2-en-1-yl]-5-pentylbenzene-1,3-diol. |
| Appearance                          | THC: Light yellow resinous oil; CBD: Light yellow resinous oil  |
| Molecular Formula                   | THC: C 21 H 30 O 2 ; CBD: C 21 H 30 O 2   |
| Molecular Mass                      | THC: 314.47; CBD: 314.47  |
| Solubility                          | THC: Soluble in methanol, ethanol, acetone, chloroform, and dichloromethane. Insoluble in water.
CBD: Soluble in methanol, ethanol, acetone, chloroform, light petroleum, and dichloromethane. Insoluble in water.   |

Tilray TIL-TC150 is formulated with THC and CBD in grape seed oil at strengths of 2 mg/ml and 100 mg/ml, respectively. The product is formulated with standard pharmaceutical excipients.

TIL-TC150 Oil is packaged in 25 ml Type III amber glass stopper bottles with a polypropylene cap and a fill of 20.0 ml. The oil drug product is stored at room temperature with a 6 months expiration.

## Figure 1. Cannabidiol Structure

CBD is highly lipid soluble and is a potent inhibitor of CYP2B6, CYP2C8, CYP2C9, CYP2C19, and CYP3A4. The effects of other concomitant drug levels metabolized by these enzyme systems are not known. CBD is excreted in the urine and faeces. The plasma peaks vary significantly between individuals but are typically between 1 to 2 hours. The CBD levels are detected up to 8 hours post administration. The adverse drug reactions of CBD that have been indicated in trials include headache, dizziness, fatigue, loss of appetite, oral numbness, dry mouth, neck pain, feeling strange, depression, lack of taste or changed taste, gastrointestinal disturbances, feeling weak, falls, shakiness, muscle stiffness, unusual dreams, nose bleeds, hot or cold flashes, and heartburn.

Cannabinoids: Increases in systolic BP over time (Sativex = 3 hrs), and decreases in diastolic BP with noted heart rate increase (Sativex = 4-8 hrs) [1] However, this is anticipated to be due to the THC content. Much of the published data refers to Sativex which contains 50% THC and many of the adverse effects are considered in keeping with the psychoactive THC effects.

Phytocannabinoids exhibit very low mammalian toxicity, and mixtures of cannabinoids are *less toxic* than pure THC. [2] Therefore, a mixture of other cannabinoids (terpenoids, etc.) may also reduce any potential toxicity issues due to having a high CBD product.

The following are the most common side effects of AEDs and/or high-THC cannabis. However, since our product is very low in THC we anticipate that these will be minor or rare:

- Dizziness, somnolence, fatigue, irritability, ataxia, blurred vision, diplopia vision, rashes, and motor incoordination / falls.
- Gastrointestinal (anorexia, loss of appetite, nausea, vomiting, and weight loss).Psychiatric and behavioural adverse reactions such as aggression, hostility, irritability, anger, and homicidal ideation / threats.

